5) Provide a summary or synopsis of the proposed study using non-technical language (not more than 1 paragraph)

[name] and associates are conducting a research study to find out more about the effectiveness of a cognitive training group intervention that provides education about cognitive, physical, and emotional changes associated with Parkinson's Disease and teaches strategies to improve cognitive skills, including attention, learning and memory, and problem-solving. The purpose of this study is to see how a cognitive training course (CogSMART) impacts thinking, mood, and quality of life in individuals who have Parkinson's disease with cognitive impairment. A subset of individuals will also participate in a pre- and post-intervention cognitive task while undergoing fMRI to assess neural changes associated with cognitive training. Additionally, some individuals will be asked to complete an adjunct exercise program either using the Wii or by participating in the Odoroki program (performing physical activity to music using a computer system). Some individuals will also be asked to provide a saliva sample (via buccal swab and/or a passive drool test) for analysis of neuroinflammatory biomarkers (e.g., cortisol, CRP, DHEA, and alpha-amylase) pre- and post-treatment, as well as DNA.

Section 6 - Specific Aims

6) Provide a statement of specific aims and hypotheses that serve as the basis for this protocol. Emphasize those aspects that justify the use of human subjects.

Phase I:

This study will investigate the effectiveness of a cognitive rehabilitation and psychoeducation program on the neuropsychological functioning of individuals with Parkinson's Disease (PD) who have cognitive impairment. The study will employ the Cognitive Symptom Management and Rehabilitation Therapy (CogSMART), a group cognitive training intervention that provides education about cognitive, physical, and emotional changes associated with PD and teaches compensatory cognitive skills (attention, learning and memory, and problem-solving) that are affected by PD.

Aim 1. To investigate the efficacy of a cognitive rehabilitation program, CogSMART, in a population of individuals with Parkinson's disease who have cognitive impairment.

Hypothesis 1a: Compared to wait-list controls, CogSMART participants will have improved cognitive functioning, functional skills and quality of life immediately following treatment.

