Hypothesis 1b: CogSMART participants will maintain their improvements at 6 months (3 months post-treatment).

Hypothesis 1c: CogSMART participants will maintain their improvements at 12 months (9 months post-treatment).

Aim 2. To investigate the vicarious effects of a cognitive rehabilitation program, CogSMART, on the caregivers of the participants.

Hypothesis 2: Compared to wait-list control caregivers, caregivers of CogSMART participants will report increased quality of life and mood immediately following their participant's treatment and 3- and 9-months post-treatment.

Exploratory Aim 1: To examine neural changes associated with the performance on an fMRI executive

function task following participation in CogSMART.

Exploratory Hypothesis 1: Compared to the non-intervention/waitlist PD participants, CogSMART completers will evidence a reduction in the dorsolateral prefrontal gyrus (due to increased cognitive efficiency) during an fMRI task of executive functioning.

Exploratory Aim 2: To investigate the feasibility and efficacy of improving visual-spatial cognition by using the Wii as an adjunct to CogSMART.

Exploratory Hypothesis 2: Compared to CogSMART (without Wii) completers, participants who use Wii as an adjunct to CogSMART (CogSMART+Wii) will demonstrate greater gains in visual spatial cognition.

Phase II:

Aim 1. Establish the efficacy of a cognitive rehabilitation program (CogSMART-PD) to improve cognition in individuals with PD-MCI.

Hypothesis 1: Compared with the supportive care control group, CogSMART-PD participants will demonstrate greater improvements in cognition at the 10-week assessment. We will examine executive function (Matrix Reasoning Test) as our primary outcome, as it is the test most sensitive to the earliest cognitive deficits in PD, impacts other cognitive functions in PD, and is a main focus of the intervention. We will examine the effects of the intervention on memory, subjective cognition, and cognitive strategy use in secondary analyses.

Aim 2. Examine the efficacy of CogSMART-PD in reducing neuropsychiatric symptoms and improving quality of life/ health status in individuals with PD-MCI.

Hypothesis 2: Compared with the supportive care control group, CogSMART-PD participants will demonstrate greater improvement in QoL/HS, and neuropsychiatric symptoms at the 10-week assessment.

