Wait-list control PD participants will continue to participate in any clinical treatment-as-usual and will receive neuropsychological assessments on the same schedule as the intervention group, though will not be receiving the treatment. At the completion of the intervention, those in the wait-list group will be invited to enter treatment if they choose. Three and nine months post-intervention (i.e., 6 and 12 months post-initiation of treatment, respectively) participants will be tested again to determine maintenance of any cognitive gains and delay of cognitive decline.

	Baseline (0 months)	0-3 months	3 months	3-6 months	6 months	12 months
CogSMART group (N=8-10)	Consent and Assessment 1 + Home Visit	CogSMART intervention	Assessment 2	No CogSMART intervention	Assessment 3	Assessment 4
Wait-list group (N=8-10)	Consent and Assessment 1 + Home Visit	No CogSMART intervention	Assessment 2	CogSMART intervention (if desired)	Assessment 3	Assessment 4

The intervention is the Cognitive Symptom Management and Rehabilitation Therapy (CogSMART), a manualized group course, predicated on a compensatory approach to cognitive difficulties where participants learn strategies to help accommodate for any cognitive weaknesses. This is a psychoeducation program, not a therapy intervention. A trained clinician(s) leads the program one time per week and each session is approximately 2 hours long. Given that this is a manualized psychoeducation program, individuals with a Bachelor's degree with training and supervision, are appropriate to lead the group class. Groups will be lead by a postdoctoral fellow and/or an appropriately trained individual who is blinded to the participants neuropsychological test results. During the first hour, psychoeducation and techniques are provided in a specific cognitive domain, and during the second hour, the skills are practiced and individualized to each participant's own situation. In this way, the intervention can be conducted in groups, allowing for participants to share strategies with each other, but the content can be individually tailored. The skills taught during the program are then generalizable to each patient's unique situation. The four targeted cognitive domains (see table below) were chosen for their relevance to everyday functioning skills and because they have been shown to be modifiable. The program will focus

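### Phase I Hypothesis 2 compares caregivers with the wait-list at months 6 and 12, after the wait-list has been offered CogSMART, so the control is no longer an intact untreated group

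*Combined protocol and SAP*

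**What the plan says.** **Wait-list access.** The Phase I schedule table (Section 9, Phase I, Procedures) has assessments at baseline and at 3, 6 and 12 months. Between months 3 and 6 the wait-list row reads "CogSMART intervention (if desired". The text above the table agrees: "At the completion of the intervention, those in the wait-list group will be invited to enter treatment if they choose". Section 10, Phase I, repeats the offer.

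**Caregiver hypothesis.** Section 6, Phase I, opens the Aim 2 hypothesis with "Hypothesis 2: Compared to wait-list control caregivers" and continues that "caregivers of CogSMART participants will report increased quality of life and mood immediately following their participant's treatment and 3- and 9-months post-treatment". Section 9 equates 3 and 9 months after the intervention with months 6 and 12.

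**Patient hypotheses.** The wait-list is the comparator immediately after treatment only: "Hypothesis 1a: Compared to wait-list controls, CogSMART participants will have improved cognitive functioning, functional skills and quality of life immediately following treatment". The 6-month statement names no comparator: "Hypothesis 1b: CogSMART participants will maintain their improvements at 6 months (3 months post-treatment". Hypothesis 1c has the same form for 12 months.

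**Analysis.** The Phase I analysis text in Section 9 names change from baseline to three months for the group comparison. It then adds repeated-measures ANCOVAs between and within groups without naming time points, and says caregiver as well as participant measures will count towards efficacy. The Procedures text gives the 6- and 12-month visits two purposes: whether gains last, and whether decline is slowed.

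**The concern.** Hypothesis 2 has three time points. At the first, the wait-list has not been offered the course. At the other two it has, and some members may have completed it. For those who took it, the 6-month visit is in effect a post-treatment assessment. Wait-list caregivers' own exposure changes too, since Section 9 invites caregivers to sit in on the classes as observers.

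Read as treated versus untreated, the later contrasts would tend to understate any lasting effect on caregivers, and a null result could be taken as absence of lasting benefit. The same risk attaches to any statement that CogSMART slows cognitive decline. In a disease whose cognition the protocol itself describes as worsening over time, that claim needs a reference course without treatment, and the schedule does not protect one beyond month 3.

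**Working it through.** There is no plan figure to reproduce. Phase I states no alpha, power, SD or numeric effect size, so the check is mainly a reading of the schedule against the hypotheses.

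**Step 1: status of the wait-list at each comparison**

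| Visit | Wait-list status | Comparison with wait-list named in Section 6 |
|---|---|---|
| 3 months | Course not yet offered | Patients (Hypothesis 1a) and caregivers (Hypothesis 2) |
| 6 months | Offered in months 3 to 6, uptake optional | Caregivers only (Hypothesis 2) |
| 12 months | As at 6 months | Caregivers only (Hypothesis 2) |

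Two of the three Hypothesis 2 comparisons therefore fall after the offer. The RM ANCOVA could extend the same contrast to patients, because its time points are left open. No section says how wait-list participants who take the course, or their caregivers, are analysed at months 6 and 12.

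**Step 2: illustration of dilution**

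Inputs:
- 10 per arm: the Phase I target for Aims 1 and 2 (Sections 9 and 10).
- Effect d = 0.5 or 0.8 SD: assumed. Section 9 says only that medium to large effects are expected, and bases this on earlier use of the programme in a psychiatric population, not on caregivers.
- Uptake c from 0 to 100%, and relative benefit r in those who cross over: assumed.
- Two-sided alpha 0.05: assumed.

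Formulas: remaining difference = d × (1 − c × r). Power in the favourable direction, by normal approximation, = Φ(remaining difference × √(n/2) − 1.96).

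Example with d = 0.5, c = 50%, r = 1: 0.5 × (1 − 0.5) = 0.25. Then 0.25 × √5 − 1.96 = −1.40, so power is about 8%.

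| Uptake (r = 1) | From d = 0.5 | Power | From d = 0.8 | Power |
|---|---|---|---|---|
| 0% | 0.50 | 20% | 0.80 | 43% |
| 25% | 0.375 | 13% | 0.60 | 27% |
| 50% | 0.25 | 8% | 0.40 | 14% |
| 75% | 0.125 | 5% | 0.20 | 7% |
| 100% | 0 | 2.5% | 0 | 2.5% |

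With half the benefit (r = 0.5) and full uptake, 0.25 and 0.40 SD remain, with power 8% and 14%. The contrast vanishes only if the whole wait-list crosses over with equal benefit.

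**Step 3: what the illustration leaves out**

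It assumes no fading in the CogSMART arm and no link between choosing the course and outcome. Uptake is the participant's choice, so the untreated remainder is self-selected, and analysing it alone would not restore the randomised comparison.

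**The case against.** The strongest reply has four parts.

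**Scope.** A reader might infer that all of Phase I's later follow-up rests on a contaminated control. The documents do not support that. Hypothesis 1a stops at the end of treatment, 1b and 1c are maintenance statements within the CogSMART arm, and the group comparison with a stated time point is at three months. This stands. The open RM ANCOVA time points are a gap, not a stated patient contrast at months 6 and 12.

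**Strength.** A reader might also infer that no untreated control remains. Uptake is optional, so an unknown part of the wait-list may stay untreated, and a comparison by assigned group remains interpretable as immediate versus deferred offer. This stands, but that is a different question from the one Hypothesis 2 asks, and the plan does not label it so.

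**Size and direction.** Effect size and uptake are assumed, and the dilution formula cannot go below zero. It therefore does not show that crossover reverses the difference, and the documents give no figure that would. This stands.

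**Value.** Phase I appears to be over: Section 9, Phase II, reports in the past tense that it had no attrition. At 10 per arm, power is only about 20% for d = 0.5 even without crossover, so a null result would say little anyway. Both facts lower the value of a change. They do not remove it, because the Phase I aims and analysis remain in the current protocol and any long-term claim would be drawn from these visits.

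**Conclusion.** The point holds in a limited form. Following Hypothesis 2 as written gives, at two of its three time points, a contrast with a partly treated and self-selected wait-list. This is a conflict between the hypothesis and the schedule, beyond a missing detail. Any between-group RM ANCOVA contrast, or inference about slowed decline, at months 6 and 12 has the same weakness.

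Phase II must not be read into this: its control group may join CogSMART-PD only after the 12-month follow-up (Section 9, Phase II, Procedures).

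The direction is dilution if the course benefits those who cross over. The amount is unknown. The importance is low: this bears on how Phase I follow-up is analysed and described, and the end-of-treatment comparison remains usable.

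**What to change.** - Limit the between-group test in Hypothesis 2, and the between-group part of the RM ANCOVA, to baseline to 3 months. Hypothesis 1a needs no change.
- Report months 6 and 12 as within-group maintenance, stating how many wait-list participants took the course and describing them by uptake.
- If the assigned groups are still compared at those visits, label the result as immediate versus deferred offer of CogSMART, and do not present it as treated versus untreated or as evidence of slowed decline.

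The cost is analysis and reporting wording, plus the long-term treated-versus-untreated claim for caregivers, which this schedule cannot support. Because Phase I appears to have run, the change should be dated and described as a clarification made afterwards. If the hypotheses are not to be reworded, a reporting caveat giving uptake and the label above is the minimum.

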Assessments: To document changes over time in both the intervention and wait-list groups, all participants will undergo neuropsychological assessment at baseline (pre-treatment), after the three month intervention period, six-months after baseline (three months from the end of the intervention), and 12 months after baseline (nine months from the end of the intervention) to determine persistence of results. The baseline assessment will entail a comprehensive neuropsychological exam consisting of measures of global cognitive functioning [Mattis Dementia Rating Scale (MDRS; Mattis, 1988), memory [California Verbal Learning Test (CVLT-II; Delis et al., 2000); Visual Reproduction Test (VRT) from the Wechsler Memory Scale-Fourth Edition (Wechsler, 2008a)], attention/concentration (Digit Span and Digit Symbol Coding from the Wechsler Adult Intelligence Scale-IV (Wechsler, 2008b)], language [Wide Range Achievement Test- Reading (WRAT-4; Wilkinson, 1993)], visuospatial skills [Judgment of Line Orientation Test (Benton et al., 1983)], executive functioning [Wisconsin Card Sorting Test-64 (WCST-64; Kongs et al., 2000); Verbal Fluency Test and Color-Word Interference Test from the Delis Kaplan Executive Functioning System (DKEFS; Delis et al., 2001); Matrix Reasoning from the WAIS-IV], mood/anxiety [Hamilton Rating Scale for Depression 17-Item (HAMD-17; Hamilton, 1960); Geriatric Depression Scale (GDS; Yesavage et al., 1982); Neuropsychiatric Inventory 14-Item version (NPI; Cummings et al., 1994); State Trait Anxiety Inventory (STAI; Spielberger et al., 1983)], functional skills [Unified Parkinson's Disease Rating Scale (UPDRS; Fahn, 1987); The Physical and Instrumental scales of the Activities of Daily living Questionnaire (IADL; Lawton and Brody, 1969)], and quality of life [Parkinson's Disease Questionnaire-39 (PDQ-39; Peto et al., 1995)]. Motor functioning will be assessed by a neurologist using the UPDRS-Part 3. The entire pre-treatment cognitive/motor assessment will take approximately three hours to complete. If participants have recently been tested clinically or as part of participation in an existing cognitive aging study, this data may be used for the baseline assessment, to reduce any unnecessary burden to the participant. In addition, all participants who consent and agree will undergo a 30-minute home evaluation. This evaluation will assess impediments to ideal cognitive and motoric functioning (e.g., organization of home) and offer strategies to improve motoric and cognitive function (e.g., use of mats/runners through doorways for cues to prevent freezing). If the participant has an identified consistent caregiver (e.g., spouse), this individual will be asked to complete several questionnaires related to their assessment of the patient's functioning (Informant Questionnaire on Cognitive Decline in the Elderly (IQCODE; Jorm and Jacomb, 1989); The Physical and Instrumental scales of the Activities of Daily living Questionnaire (IADL; Lawton and Brody, 1969), NPI – informant version) and quality of life (PDQ-39 proxy form), their ratings of their own level of burden regarding caregiving [Caregiver Burden Inventory; (CBI; Novak and Guest, 1989)], and their self-reported mood [HAMD-17, GDS; and STAI]. The caregiver questionnaires are estimated to take approximately 30-40 minutes to complete.

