
At post-treatment and 6-month (3 months post-intervention) follow-up, participants will be administered the Mattis Dementia Rating Scale (MDRS; Mattis, 1988), California Verbal Learning Test – II (CVLT-II; Delis et al., 2000), Digit Span and Digit Symbol Coding from the WAIS-IV (Wechsler, 2003), Verbal Fluency and the Color-Word Interference tests from the Delis Kaplan Executive Functioning System (Delis et al., 2001), Matrix Reasoning from the WAIS-IV, the Geriatric Depression Scale (Yesavage et al., 1982), Hamilton Rating Scale for Depression 17-Item (HAMD-17; Hamilton, 1960), Neuropsychiatric Inventory 14-Item version (NPI; Cummings et al., 1994); State Trait Anxiety Inventory (STAI; Spielberger et al., 1983), The Physical and Instrumental scales of the Activities of Daily living Questionnaire (IADL; Lawton and Brody, 1969), and the Parkinson's Disease Questionnaire-39 (PDQ-39; Peto et al., 1995). These follow-up assessments will take approximately 2 hours to complete. Caregivers will be asked to complete the Informant Questionnaire on Cognitive Decline in the Elderly (IQCODE; Jorm and Jacomb, 1989), the PADL and IADL scales – informant version, the PDQ-39 proxy form, the Caregiver Burden Inventory (CBI; Novak and Guest, 1989), and the Hamilton Rating Scale for Depression 17-Item (HAMD-17; Hamilton, 1960), Geriatric Depression Scale (GDS; Yesavage et al., 1982), and the State Trait Anxiety Inventory (STAI; Spielberger et al., 1983). We will use counterbalanced alternate forms of the tests included in the neuropsychological assessment, when available, to partially address practice effects. At 12 months (9 months post-intervention), participants will be given the entirety of the battery they completed at baseline. Standardized alternative forms that measure the same or similar cognitive abilities may be substituted for the aforementioned tests if warranted to prevent practice effects, fatigue, or participant attrition.

All data will have quality control measures applied. All neuropsychological assessments will be double-scored to ensure accuracy. Data will be compiled in a database and all data will be double entered to preserve the integrity of the database. The subjects' confidentiality will be strictly maintained in data storage, analysis, and presentation.

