Our projected sample size is consistent with the sample reported on in the preliminary data section ([name] et al., 2008). As we propose to use a similar sample size and the same cognitive rehabilitation program, we anticipate achieving similar medium to large effect sizes in the proposed study. To determine whether CogSMART will improve cognition in PD, we will employ statistical analyses including reliable change indexes to take into account change in neuropsychological test scores over the course of the intervention while also accounting for predicted practice effects. We will compare the treatment and control groups on baseline and three-month change scores. Group comparisons of differences and

changes in neuropsychological test scores between as well as within groups will also be determined via repeated measures (RM) ANCOVAs. Cognitive, functional, and quality of life indices of both participants and caregivers will be of interest in determining efficacy of treatment.

As an exploratory aim, we will recruit 60 additional individuals to complete the protocol as described above and in addition, participate in two (pre/post) hour-long brain imaging (fMRI) sessions. The imaging sessions will consist of a structural brain scanning and participation in an fMRI cognitive task (please see below). Following the baseline evaluation, half of the participants will be randomly assigned to the intervention group ($n = 30$) and participate in the CogSMART program. The groups will be broken up to consist of 8-10 individuals. The remaining participants ($n = 30$) will be assigned to the non-intervention /waitlist ("care-as-usual") group. This group will also be broken down into groups of 8-10 when enrolled in the intervention. Participants will be retested by a group assignment-blinded examiner on the clinical and cognitive battery and imaging protocol following the intervention or waitlist.

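### Phase I lists three unranked analyses of cognition, and none is stated to adjust the month-3 score for its own baseline

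*Combined protocol and SAP*

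**What the plan says.** The Phase I analysis paragraph in Section 9 (Design and Methods) names three approaches to cognition:

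1. Reliable change indexes: "reliable change indexes to take into account change in neuropsychological test scores over the course of the intervention while also accounting for predicted practice effects". No formula, cut-off, source for the predicted gain or group-level test is given.
2. A between-arm contrast: "We will compare the treatment and control groups on baseline and three-month change scores".
3. Repeated-measures models: "changes in neuropsychological test scores between as well as within groups will also be determined via repeated measures (RM) ANCOVAs". The covariates are not named.

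None of the three is ranked above the others.

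The same section describes the data available. On the baseline: "all participants will undergo neuropsychological assessment at baseline (pre-treatment), after the three month intervention period". The wait-list arm "will receive neuropsychological assessments on the same schedule as the intervention group". After that period the control is no longer untreated: "At the completion of the intervention, those in the wait-list group will be invited to enter treatment if they choose". On practice: "We will use counterbalanced alternate forms of the tests included in the neuropsychological assessment, when available, to partially address practice effects". Where a participant was recently tested elsewhere, "this data may be used for the baseline assessment, to reduce any unnecessary burden to the participant".

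Section 10 gives the final Phase I sample for Aims 1 and 2 as 20, with 10 per arm. Section 9 assigns the arms by alternating ID numbers.

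**The concern.** The design has what an efficient comparison needs: a baseline score in both arms and a control arm tested at the same times. The plan does not commit to the analysis that uses them best, which is the month-3 score by arm adjusted for the baseline score.

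Three things follow.

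- **Precision.** A raw change score fixes the weight on baseline at 1. When the pre/post correlation is below 1, that is too much weight. Precision is lost, and part of any baseline difference between the arms appears in the estimated effect.
- **Practice.** A predicted practice gain is a substitute for a control group. The wait-list arm already measures practice in the trial's own patients, on the same forms and at the same intervals.
- **Choice of result.** With three unranked methods, two of them incompletely defined, the reported analysis can be chosen after the results are known.

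**Working it through.** **Inputs from the plan.** The sample is 10 per arm (Section 10, Phase I). The effect is described only as medium to large, with no number (Section 9, Phase I). Phase I states no alpha, power, SD or pre/post correlation, and it rests its size on similarity to an earlier sample. There is therefore no power figure to reproduce.

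**Assumptions.** d = 0.8 in SD units of the test score; two-sided alpha 0.05; equal variances before and after; pre/post correlation r = 0.6 to 0.8.

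**1. Precision.** In units of the score variance, the residual variance is 2(1 − r) for a change score and 1 − r² for baseline-adjusted ANCOVA. The ratio is (1 + r)/2, which is 0.80, 0.85 and 0.90 at r = 0.6, 0.7 and 0.8. ANCOVA must also estimate the slope. With 20 people this multiplies the variance of the treatment estimate by about 1 + 1/(20 − 4) = 1.0625. The realised ratios are:

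- r = 0.6: 0.80 × 1.0625 = 0.85
- r = 0.7: 0.85 × 1.0625 = 0.90
- r = 0.8: 0.90 × 1.0625 = 0.96

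The variance is therefore about 5 to 15% lower with ANCOVA.

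**2. Power at 10 per arm, d = 0.8.** The change-score figures agree with the noncentral t on 18 df. The ANCOVA figures come from simulating the actual t-test on 17 df. A noncentral-t formula that ignores slope estimation gives 56, 66 and 80%, slightly too high at this size.

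| r | Change score | Baseline-adjusted ANCOVA |
|---|---|---|
| 0.6 | 47% | 54% |
| 0.7 | 59% | 63% |
| 0.8 | 76% | 78% |

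**3. Baseline differences.** With 10 per arm, and treating assignment as if random, the difference in baseline means has an SD of √(2/10) = 0.45 score SDs. Given a baseline difference D, the change-score contrast is shifted by −(1 − r)D. For D = 0.45 this is 0.4 × 0.45 = 0.18 SD at r = 0.6 and 0.2 × 0.45 = 0.09 SD at r = 0.8. Adjusting for baseline removes this shift, apart from error in the estimated slope.

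**4. Repeated-measures ANCOVA.** If baseline enters as one of the repeated measurements and only two time points are used, the arm-by-time test, before any other covariates, is the change-score test again. If baseline enters as a covariate, it is the adjusted comparison. The plan does not say which.

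**5. Reliable change, if used to classify people.** This needs further assumptions: improved means change above 1.645 SDs of change, the predicted practice gain is correct, and the arms are compared by Fisher's exact test. The proportion improved is 5% in controls and 1 − Φ(1.645 − 0.8/√(2(1 − r))) in the treated arm. That is 23%, 27% and 35% at r = 0.6, 0.7 and 0.8. Exact power is 3%, 6% and 16%.

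**The case against.** Several stronger readings are tempting, and the documents do not support them.

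**The plan ignores its control arm.** It does not. The change scores are compared between treatment and control, and the repeated-measures models also compare groups.

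**Baseline adjustment is ruled out.** It is not. The ANCOVA covariates are unnamed, so adjustment for baseline is unspecified, neither stated nor excluded.

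**The reliable change analysis has almost no power.** The 3 to 16% in step 5 applies only to classified outcomes. The plan states no cut-off, no classification and no such test. An index with a constant practice term, kept continuous and compared between arms, is a rescaled change score with the same 47 to 76% power.

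**Practice is removed twice, once by alternate forms and again by prediction.** This would require the predicted gain to come from same-form retesting, and the plan gives no source. It also says that alternate forms are used only where available and deal with practice only in part, so some practice remains to be corrected. A constant common to both arms cancels in a between-arm comparison in any case.

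**Baseline adjustment is much stronger than change scores.** At this size the gain is about 2 to 7 percentage points.

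A fair objection also concerns timing. The Phase II participants paragraph in Section 9 reports, in the past tense, that Phase I had no attrition. Phase I data may therefore already exist, and a lead analysis named now may not be a true prespecification. That stands. It limits what the fix can claim, but does not remove the reason for making it.

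**Conclusion.** The point holds as a gap in specification with a modest loss of efficiency. Three analyses are listed without rank, the reliable change index is undefined, the ANCOVA covariates are missing, and the one fully described between-arm contrast is the less precise one.

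Under the assumed d, alpha and r, naming the baseline-adjusted comparison lowers the variance by about 5 to 15% and raises power by a few points, most at the lower correlations. A correlation at the low end is more plausible where earlier testing stands in for the baseline, because the interval is then longer and varies between people. Protection against baseline differences matters as much as power, with 10 per arm and alternation in place of random assignment.

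The documents do not show that the Phase I comparison is invalid, or that the index-based analysis would have near-zero power. The power figures depend on values that Phase I does not state.

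**What to change.** In the Phase I analysis paragraph of Section 9:

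- Name one lead analysis of cognition: the month-3 score by arm, adjusted for the same test's baseline score, reported as a difference with a 95% CI. Month 3 is the right time point because wait-list members may start CogSMART afterwards.
- State the covariates of the repeated-measures ANCOVAs and call those models supporting.
- Keep reliable change indexes as description only. Give the formula, and use the wait-list arm's mean change as the practice term.
- If Phase I data have already been seen, say in the plan and in any report that this analysis was specified after data collection.

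The cost is a few sentences. The lead analysis needs no new data, visits or participants, since both scores are already planned in both arms.
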